15.3 Clinical Laboratory Evaluation

Clinical laboratory evaluation will be collected on the 'Local Laboratory Results: Hematology' and 'Local Laboratory Results: Chemistry' eCRF pages.

Laboratory values (including corresponding normal ranges) from the local labs will be used for summary statistics and shift tables.

Quantitative laboratory parameters reported as "< X", below the lower limit of quantification (BLQ), "> X" or above the upper limit of quantification (ULQ), will be converted to X/lower

limit/upper limit for the purpose of quantitative summaries (with the exception of eGFR), but will be presented as recorded, i.e. as “< X”, BLQ, “> X” or ULQ in listings.

The full list of parameters with NCI-CTCAE grades available and not available and relevant directions of abnormalities of interest are listed in Appendix 1 at section 18.1.

Laboratory results will be classified according to the NCI-CTCAE criteria version 5.0. Some of the toxicity gradings are based on laboratory measurements in conjunction with clinical findings. Non-numerical qualifiers will not be taken into consideration in the derivation of CTCAE criteria (e.g., hypokalemia Grade 1 and Grade 2 are only distinguished by a non-numerical qualifier and therefore Grade 2 will not be derived).

Additional laboratory results that are not part of NCI-CTCAE will be presented according to the categories: below normal limit, within normal limits and above normal limit (according to the laboratory normal ranges).

For estimated glomerular filtration rate (mL/min/1.73 m²) the value collected in CRF will be used when reported. When missing or reported as “>/<X”, it will be calculated using the Modification of Diet in Renal Disease equation:

$$\text{eGFR} = 175 \times (\text{serum creatinine in mg/dL})^{-1.154} \times (\text{age in years})^{-0.203} \times 0.742 \text{ (if female)} \times 1.212 \text{ (if race is black)}$$

The following summaries will be provided by treatment group for each of chemistry and

hematology laboratory:

All parameters:

- Summary results based on normal ranges by time points will include number and percentage of participants below normal limit, within normal limits and above normal limit.

Non-gradable parameters according to NCI-CTCAE:

- Shift from baseline to the worst on-treatment value according to normal range criteria

Gradable parameters according to NCI-CTCAE:

- Shift from baseline to the worst on-treatment value for each relevant directionality (minimum and/or maximum value) according to the CTCAE toxicity grades; the highest CTCAE grade during the on-treatment period is considered as the worst grade for the summary
- Summary results based on CTCAE grade by time point will include number and percentage of participants with Grade 1, 2, 3, 4, 3/4, and any grade (1 to 4).

For those parameters which are graded with two directions of toxicities such as potassium (hypokalemia/hyperkalemia), the toxicities will be summarized separately. Low direction toxicity (e.g., hypokalemia) grades at baseline and post baseline will be set to 0 when the variables are derived for summarizing high direction toxicity (e.g., hyperkalemia), and vice versa.

Spaghetti plots for Aspartate Aminotransferase, Alanine Aminotransferase and Total Bilirubin, will be presented by treatment group, including only those participants with any NCI CTCAE grade 2 or higher at any point in time during the study.

The listings of laboratory results will be provided for all laboratory parameters. The listings will be sorted by actual treatment, then subject ID, parameters and assessment dates for each participant. Laboratory values that are outside the normal range will also be flagged in the data listings, along with corresponding normal ranges and CTCAE grades. A listing for laboratory normal ranges will also be provided.

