9.3 Definition of Baseline and Change from Baseline

In general, the last non-missing measurement prior to first dose will serve as baseline measurement.

Unless otherwise specified, if a scheduled pre-dose measurement actually occurred post-dose, then the corresponding measurement will be analyzed similar to an unscheduled post-dose measurement.

Absolute and percent changes from baseline are defined as:

absolute change = analysis visit value – baseline value

percent change = $100 * (\text{analysis visit value} - \text{baseline value}) / \text{baseline value}$

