9.9 Analysis visit windows

For endpoints to be reported by visit, the following analysis visit windows will be defined:

- Baseline (see Section 9.3 for definition)
- Analysis Day 2
- Analysis Day 3
- Analysis Day 4
- Analysis Day 5: Day 5 and 6
- Analysis Day 7: Day 7 and 8
- Analysis Day 10: from Day 9 to Day 11
- Analysis Day 14: from Day 12 to Day 17
- Analysis Day 21: from Day 18 to Day 24
- Analysis Day 28: from Day 25 to Day 35
- Analysis Day 44: from Day 36 to Day 52
- Analysis Day 60: from Day 53 onwards

In case of multiple assessments collected within the same window, the one closest to the target date will be used for summary statistics. All the assessments will be used for worst case analyses.

10 Study Participants

The subsections in this section include specifications for reporting participant disposition and study treatment/study discontinuations. Additionally, procedures for reporting protocol deviations are provided.

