11.1 Demographics

Demographic characteristics and physical measurements will be summarized descriptively using the following information from the ‘Demography’ and ‘Screening Vital Signs’ eCRF pages.

The following demographic characteristics will be included:

- Sex: male, female
- Race: white, black or African American, Asian/ Pacific Islander, American Indian or Alaska Native, more than one race, other, unknown
- Ethnic origin: Hispanic or Latino/Not Hispanic or Latino
- Age (years)
- Age categories:
 - < 60 years,
 - ≥ 60 years
- Country: Brazil, Philippines, United States of America
- Site
- Height (cm) at Baseline

- Weight (kg) at Baseline
- BMI (kg/m²) at Baseline
 - < 30 kg/m²,
 - ≥ 30 kg/m²

Specifications for computation:

- Age [years]
 - (date of given informed consent - date of birth + 1) / 365.25
 - In case of missing day for at least one date, but month and year available for both dates: For the derivation of age, the day of informed consent and the day of birth will be set to 1 and the formula above will be used
 - In case of missing month for at least one date, but year available for both dates: For the derivation of age, the day and the month of informed consent and the day and month of birth will be set to 1 and the formula above will be used

The integer part of the calculated age will be used for reporting purposes.

- BMI [kg/m²] = $\frac{\text{weight [kg]}}{\text{height[cm]}^2} \times 10000$

All demographic data will be reported in listings.

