| | Aspartate Aminotransferase (AST) | Aspartate Aminotransferase increased | High |
| | Alkaline Phosphatase (ALP) | Alkaline Phosphatase increased | High |
| | Bicarbonate | Blood Bicarbonate decreased | Low |
| | Total Bilirubin | Blood bilirubin increased | High |
| | Creatinine | Creatinine increased | High |
| | Creatine Kinase (CK) | CPK increased | High |
| | Sodium | Hyponatremia / Hypernatremia | Low / High |
| | Potassium | Hypokalemia / Hyperkalemia | Low / High |
| | Glucose | Hypoglycemia | Low |

Note: parameters with both Low and High directions of abnormality are going to be split. For example, Calcium is going to be split in Calcium Low and Calcium High.

NCI-CTC non-gradable parameters

| Laboratory Assessment | Parameters | Direction of interest |
|-----------------------|------------|-----------------------|
| Hematology | Hematocrit | |

| Laboratory Assessment | Parameters | Direction of interest |
|------------------------------|---|------------------------------|
| | Mean corpuscular volume (MCV) | High |
| | Basophils | |
| | Monocytes | High |
| Biochemistry | Total Protein | Low |
| | Chloride | High |
| | Urea Nitrogen (BUN) | High |
| | Estimated Glomerular Filtration Rate (eGFR) | Low |

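### The eGFR tables can mix the local laboratory's equation with an MDRD fallback within one participant, so a single visit without a numeric chart eGFR can create or hide a normal-range shift

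*SAP*

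**What the plan says.** SAP 15.3 gives eGFR its own rule. The first choice is the recorded value: "For estimated glomerular filtration rate (mL/min/1.73 m²) the value collected in CRF will be used when reported". When that value is missing, or recorded only as greater or less than some X, "it will be calculated using the Modification of Diet in Renal Disease equation". The formula printed there has the same coefficients as Protocol 5.2, exclusion criterion 18. For other parameters, a result recorded as beyond a bound is set to the bound; eGFR is excepted and goes to the fallback.

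Protocol 1.2 puts creatinine and eGFR on the same routine chemistry panel, run by the local laboratory and recorded from the chart. No equation is given for the chart eGFR. Apart from the fallback, MDRD is tied to eGFR only in exclusion criterion 18.

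SAP Appendix 1 (18.1) lists eGFR as non-gradable with Low as the direction of interest. It therefore enters the table described in SAP 15.3 as "Shift from baseline to the worst on-treatment value according to normal range criteria", using local normal ranges, and the summary of values below, within and above range by time point. Under SAP 9.3, "the last non-missing measurement prior to first dose will serve as baseline measurement". Under SAP 9.9, "All the assessments will be used for worst case analyses". Neither section asks for baseline and worst value to come from the same equation.

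**The concern.** A shift table compares a participant with himself, so both ends of the comparison need to be on one scale. Here the scale can change at any visit where the laboratory returned creatinine but no numeric eGFR. Close to the lower limit, a difference between equations can then look like a change in kidney function, or cover one up. The lowest on-treatment value decides the participant's category, so one such visit can decide the entry.

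At stake are individual cells of one descriptive safety row. Safety is a primary objective of the study and includes clinically significant laboratory changes, so an odd entry in this row would be read with some care.

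**Working it through.** The plan states no figure for this point, so there is nothing to reproduce. The check uses the SAP's own formula and one assumed quantity.

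**Inputs**
- MDRD (SAP 15.3; Protocol 5.2, criterion 18): eGFR = 175 × Cr^-1.154 × age^-0.203, × 0.742 if female, × 1.212 if race is black.
- r = chart eGFR / MDRD at the same creatinine. Not in the documents; assumed, range 0.90 to 1.20.
- Lower limit of normal for eGFR. Not in the documents; 60 assumed, with 90 as an alternative.

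**Local equation reads higher (r > 1): false fall**

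Man aged 55, no race factor, creatinine constant at 1.3 mg/dL:
- 1.3^-1.154 = 0.7388 and 55^-0.203 = 0.4433.
- MDRD = 175 × 0.7388 × 0.4433 = 57.3.
- Chart value at r = 1.10: 57.3 × 1.10 = 63.0.

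Baseline and all other visits are taken from the chart at 63.0, within range. The one visit without a chart eGFR is scored 57.3, below range, and becomes the worst value. The table records normal to low although creatinine did not move.

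In general the two sources disagree when MDRD lies between limit / r and the limit:

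| r | Limit 60 | Limit 90 |
|---|---|---|
| 1.05 | 57.1 to 60 | 85.7 to 90 |
| 1.10 | 54.5 to 60 | 81.8 to 90 |
| 1.20 | 50.0 to 60 | 75.0 to 90 |

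**Local equation reads lower (r < 1): hidden fall**

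Man aged 60, no race factor, creatinine 1.0 mg/dL at baseline and 1.2 at one visit that has no chart eGFR:
- 60^-0.203 = 0.4355. At creatinine 1.0, MDRD = 175 × 0.4355 = 76.2; the chart gives 68.6 (r = 0.90) or 72.4 (r = 0.95), within range.
- At creatinine 1.2, 1.2^-1.154 = 0.8103 and MDRD = 76.2 × 0.8103 = 61.8, within range. The chart would have given 55.6 (r = 0.90) or 58.7 (r = 0.95), below range.

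If the fall occurred only at that visit, the table shows no shift. The disagreement band is limit to limit / r: 60 to 66.7 (r = 0.90) or 60 to 63.2 (r = 0.95); at limit 90, 90 to 100 or 90 to 94.7.

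**With one equation throughout**

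If MDRD is used at baseline and at every visit, r = 1 and the bands have zero width. The man aged 55 is 57.3 at every visit, and no shift is recorded. Age is computed once, at informed consent (SAP 11.1), so unchanged creatinine gives exactly the same eGFR.

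**The case against.** **Several conditions must hold together.** The local equation must differ from MDRD. Creatinine must be present without a numeric eGFR, although both are on one panel. The value must lie in a narrow band, and no other visit may already decide the category. All of this stands. A laboratory that never reports eGFR gives MDRD at every visit, so nothing is mixed. At a laboratory that reports only a bound above 60, with 60 as its limit, every within-range value goes to the fallback, so the first example cannot arise there.

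**Using the recorded value and deriving only the gaps is the SAP's convention elsewhere.** SAP 15.5 does the same for QTcF. That is fair, but QTcF is one named formula, so recorded and derived values are meant to agree. For eGFR the recorded value has no named formula.

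**The consequences are small.** This also stands. SAP section 9 treats all tests as exploratory, creatinine is graded separately by CTCAE, and "The listings of laboratory results will be provided for all laboratory parameters", with results beyond a bound shown as recorded.

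A reader might infer more than the documents support:
- *That a baseline recorded only as above a bound, and replaced by a lower MDRD value, is the same fault.* It is a disagreement between MDRD and the chart about baseline status. MDRD at every visit keeps that baseline, so the entry stays below to below.
- *That no rule covers the race categories "American Indian or Alaska Native, more than one race, other, unknown".* The factor applies only if race is black, so a participant coded as other or unknown does not get it. Only more than one race is unclear.
- *That a number of affected participants per arm can be given.* The documents supply no r, no lower limit and no share of visits lacking a chart eGFR, and missing values may cluster by laboratory.

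**Conclusion.** The point holds in a narrow form, as a low-priority improvement. SAP 15.3 allows a participant's baseline and worst eGFR to come from different equations, and one on-treatment visit is enough to create a false shift or hide a fall.

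The size depends on two things the documents do not give: the local equations and the local lower limits. If every site reports this MDRD form, the effect is nil. If a local equation differs by 5 to 10%, the affected band at limit 60 is about 3 to 7 eGFR units wide (57.1 to 60 at the narrowest, 60 to 66.7 at the widest). How many participants fall in it with a qualifying visit cannot be estimated.

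Two further readings should be resisted. The rule gives no reason to expect bias between arms: allocation is randomised and sites are blinded, so the noise should be non-differential. Nor does the rule touch eligibility, the on-study eGFR stopping criterion or any efficacy result, because it governs only how values are tabulated.

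**What to change.** In SAP 15.3, for the eGFR normal-range and shift tables, calculate MDRD with the exclusion criterion 18 equation from recorded creatinine at baseline and at every visit. Apply one fixed race factor per participant, and state how more than one race is handled. Keep the chart eGFR in the laboratory listings. A common lower limit is not needed to remove the mixing, so the local ranges can stay.

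The cost is a sentence or two in the SAP and a small programming change. Creatinine, age, sex and race are already collected. The main downside is that the tabulated eGFR may differ from the value the site saw. A visit with a chart eGFR but no creatinine would also drop out of the eGFR tables, which should be rare as the two share a panel. The race convention is a judgement, but because it is constant within a participant it cannot itself create a shift.

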8.1 Temporary or Permanent Discontinuation of the Study Intervention for Toxicity

Any new clinically relevant finding is reported as an AE graded according to Common Terminology Criteria for Adverse Events (CTCAE) Version 5.0.

Participants who have their study intervention held for suspected drug toxicity, may have the study intervention restarted with approval of the Sponsor if the potential benefit of the study intervention outweighs the risk of the toxicity. More specifically, if a clinically significant finding is identified after enrollment, the Investigator or qualified designee will determine if the participant can continue on the study intervention and if any change in participant management is needed in discussion with the Medical Monitor and Sponsor.

The study intervention may not be restarted if any SAE, clinically significant AE, persistent Grade 4 laboratory abnormality, intercurrent illness, or other medical condition occurs indicating to the Investigator that continued participation is not in the best interest of the participant.

- The study intervention will not be restarted if the following occurs: serious infection other than COVID-19, seizure, clinically significant arrhythmia, or serotonin syndrome.
- The study intervention should be withheld if the participant develops Grade 3 liver function tests (i.e., an increase in transaminases [ALT or AST] > 5.0 to $20.0 \times$ ULN if Baseline was normal or > 5.0 to $20.0 \times$ Baseline if Baseline was abnormal regardless of the participants bilirubin level). If the ALT and AST do not immediately trend to the participant's Baseline values within 24 hours, the study intervention must be held until the liver function tests return to the participant's Baseline values. If the ALT and AST return to the participant's Baseline values before Day 15, the study intervention may be restarted.
- For participants whose eGFR < 40 mL/min/1.73 m² for 24 hours, experience a Grade 3 increase in serum creatinine ($> 3.0 \times$ Baseline or > 3.0 to $6.0 \times$ ULN) for 24 hours or who develop Acute Kidney Injury (requiring hemodialysis), the study intervention must be permanently discontinued.

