10.4.4 Safety Analysis

Adverse events will be coded according to the Medical Dictionary for Regulatory Activities (MedDRA). The number and percentage of participants experiencing 1 or more treatment-emergent adverse events (TEAEs) will be summarized according to MedDRA system organ classes and preferred terms by treatment group, relationship to study intervention, and severity.

Deaths, SAEs, AESIs, TEAEs leading to treatment discontinuation, and TEAEs leading to treatment interruption will be summarized by treatment group.

Summary statistics will be used to present observed values and changes from Baseline in vital signs, ECG parameters, and abnormal laboratory parameters.

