5.2 Part B Objectives

| OBJECTIVES | ENDPOINTS (OUTCOME MEASURES) | IAP SECTIONS |
|---|--|---|
| Primary Efficacy | | |
| To evaluate the time to recovery in participants hospitalized due to COVID-19 pneumonia with M5049 compared to placebo. | Time to recovery from Day 1 through Day 28, defined as time from Day 1 to first occurrence of WHO 9-point ordinal scale 3 or less. | 14.1 |
| Primary Safety | | |
| To assess the safety of M5049 compared to placebo. | 
 Incidence of TEAEs, AESIs, TEAEs leading to treatment discontinuation, and SAEs from Day 1 through Day 60. Clinically significant changes in laboratory parameters and ECGs from Day 1 through Day 28. | 
 15.1 15.3 and 15.5 |
| Secondary | | |
| To assess the proportion of participants free of respiratory support with M5049 compared to placebo. | Alive and not requiring supplemental oxygenation (including any supplemental oxygen, noninvasive or mechanical ventilation and ECMO) through Day 28. | 14.2.1 |
| To evaluate the change in clinical status with M5049 compared to placebo. | 
Clinical status from Day 1 through Day 60 (on a 9-point ordinal scale):
 
 0. Uninfected: no clinical or virological evidence of infection. 1. Ambulatory: no limitation of activities. 2. Ambulatory: limitation of activities. 3. Hospitalized, mild disease: hospitalized, no oxygen therapy. 4. Hospitalized, mild disease: oxygen by mask or nasal prongs. 5. Hospitalized, severe disease: noninvasive ventilation or high flow-oxygen. 6. Hospitalized, severe disease: intubation and mechanical ventilation. 7. Hospitalized, severe disease: ventilation + additional organ support – e.g., pressors, RRT, ECMO. 8. Death. | 14.2.2 |
| To assess normalization of oxygenation status with M5049 compared to placebo in participants who are alive and not on mechanical ventilation. | 
Time to SpO₂ of ≥ 94% sustained for at least 24 hours in room air from Day 1 through Day 28.
 
Further referred as “time to SpO₂ improvement”
 | 14.2.3 |

| OBJECTIVES | ENDPOINTS (OUTCOME MEASURES) | IAP SECTIONS |
|---|--|--|
| To evaluate the numbers of deaths with M5049 compared to placebo. | All-cause mortality (Day 1 through Day 60). | 14.2.4 |

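### SAP 15.3 lists no change-from-baseline laboratory table, so the by-arm eGFR tables cannot show how far eGFR falls or whether it passes the protocol's threshold of 40

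*SAP*

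**What the plan says.** **Protocol.** Section 10.4.4 states: "Summary statistics will be used to present observed values and changes from Baseline in vital signs, ECG parameters, and abnormal laboratory parameters". Exclusion criterion 18 removes people with eGFR below 45 mL/min/1.73 m². Section 8.1 provides that if eGFR is below 40 for 24 hours, "the study intervention must be permanently discontinued". Separate limbs of the same rule cover a Grade 3 creatinine rise lasting 24 hours and acute kidney injury.

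**SAP.** Section 5.2 maps the primary safety endpoint "Clinically significant changes in laboratory parameters and ECGs from Day 1 through Day 28" to Section 15.3 for laboratory data. Section 15.3 opens by saying "Laboratory values (including corresponding normal ranges) from the local labs will be used for summary statistics and shift tables", then itemises the tables:

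- For every test: how many participants, with percentages, lie under, inside or over the local normal range at each time point.
- Non-gradable parameters: "Shift from baseline to the worst on-treatment value according to normal range criteria".
- Gradable parameters: CTCAE grade shifts and grade counts by time point.
- Spaghetti plots for AST, ALT and total bilirubin only.

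Appendix 1 (SAP 18.1) puts eGFR in the non-gradable table, with low as the direction of interest. Section 7, on departures from the protocol, deals only with stratification factors.

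**The concern.** The protocol names three kinds of safety data for which change from baseline will be summarised. The SAP lists that summary for two of them, vital signs (15.4) and ECG (15.5), but not for laboratory data. Nothing says the difference is intended.

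eGFR is the most exposed parameter. It has its own limit in the permanent-discontinuation rule, yet no CTCAE table applies to it and no SAP table uses the value 40. What remains is a three-way classification against local normal ranges, which does not record how far a value moves. In a trial of two doses against placebo, a by-arm summary of the size of change is the basic means of seeing a dose-related renal effect. Without it, a primary safety endpoint rests, for eGFR, on tables that can treat a trivial fall and a large one alike.

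**Working it through.** There is no planned figure to reproduce. The check sets the lists side by side, classifies example values, and inverts the eGFR formula.

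**1. Planned outputs**

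| Data | Protocol 10.4.4 | SAP list of outputs |
|---|---|---|
| Vital signs | observed and change | observed and change (15.4) |
| ECG | observed and change | observed and change (15.5) |
| Abnormal laboratory parameters | observed and change | none listed (15.3) |

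**2. Classification of a lowest value of 39**

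Inputs: entry eGFR of 45 or more (protocol 5.2) and a threshold of 40 (protocol 8.1). The lower normal limit is an assumption, because the local laboratories supply it and neither document states one. Values from 40 to 90 were tried, and also the case of no limit.

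| Assumed lower limit | Entry eGFR | Shift-table cell |
|---|---|---|
| 40 or 45 | 45 or more | normal to low |
| 60 | 45 to below 60 | low to low |
| 60 | 60 or more | normal to low |
| 75 | 45 to below 75 | low to low |
| 90 | 45 to below 90 | low to low |
| none supplied | any | no category |

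The last row could arise where a laboratory does not report eGFR. The SAP then calculates it but does not say which reference range applies.

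With a limit of 60, falls of 59 to 58 and 59 to 39 share the low-to-low cell, and 65 to 59 and 65 to 39 share the normal-to-low cell. So the size of the fall is lost even where a shift is visible.

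**3. Does the creatinine table stand in for eGFR?**

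The MDRD formula (protocol 5.2, SAP 15.3) makes eGFR proportional to creatinine^(−1.154). The creatinine ratio for a fall from eGFR B to W is therefore (B/W)^(1/1.154).

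- 45 to 39: (45/39)^(1/1.154) = 1.13-fold.
- 58 to 39: (58/39)^(1/1.154) = 1.41-fold.

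The protocol's Grade 3 baseline limb is a rise above 3.0 times baseline. A threefold rise ends at eGFR 40 only from a baseline of 40 × 3^1.154 ≈ 142. From lower starting values, eGFR passes 40 well before that limb is reached. The limb based on the upper normal limit cannot be computed, because the documents give no such limit. The boundaries of Grades 1 and 2 are not given either, so this step does not show that the lower creatinine grades would miss these cases.

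**4. What a change-from-baseline table would show for a fall to 39.9**

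- From 45: −5.1 (−11.3%).
- From 60: −20.1 (−33.5%).
- From 90: −50.1 (−55.7%).

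**The case against.** The best defence is that the numeric summary is intended and merely unlisted. SAP 6.3 speaks of performing all analyses identified in the protocol and the SAP. Section 9.1 gives statistics for continuous variables, 9.3 defines change from baseline, and 9.9 sets visit windows. Section 15.3 itself mentions summary statistics, and it replaces a missing or inequality-coded eGFR with a calculated number. This makes oversight more likely than deliberate removal, and a reader should not infer that the sponsor chose to drop the analysis. It does not supply the table. The sentence in 6.3 goes on to make the analyses wait for the end of follow-up, so it governs timing. Sections 9.1, 9.3 and 9.9 say how to summarise, not what. The specific list is in 15.3.

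Three stronger readings are tempting, and the documents do not support them:

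- *That a fall below 40 would be invisible.* Every result is listed by treatment with out-of-range values flagged. Creatinine has grade tables by arm. A stop would count among treatment discontinuations by reason, and among adverse events leading to discontinuation if recorded as one. This cover is real but indirect: listings do not compare arms, and the adverse-event tables depend on reporting.
- *That the protocol promises change from baseline for every laboratory test.* It says abnormal parameters.
- *That any value below 40 triggers the stop.* The rule requires 24 hours.

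It is also fair to say that the study is exploratory and that normal-range shifts are a usual choice for ungraded tests. That supports keeping those tables. It does not explain leaving out the one the protocol describes.

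**Conclusion.** The point holds as a mismatch between protocol and SAP with a practical consequence for eGFR. The mismatch needs no assumption: protocol 10.4.4 states a laboratory summary that SAP 15.3 does not list and Section 7 does not explain.

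The consequence depends partly on the local lower normal limit. Low to low arises only for limits above 45; from 40 to 45 the same fall shows as normal to low. The loss of the size of the fall does not depend on which of these applies. How many participants would be affected cannot be estimated, because the documents do not give the distribution of entry eGFR.

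This should be corrected because it concerns a primary safety endpoint and is cheap to repair. It does not affect the efficacy analyses, and it does not mean that individual renal events would go unrecorded.

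**What to change.** In SAP 15.3 add:

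1. Observed value and change from baseline by analysis visit and treatment group, at least for the abnormal laboratory parameters named in protocol 10.4.4, and including eGFR. This table also serves calculated eGFR values that have no reference range.
2. For eGFR, a by-arm shift from baseline to lowest on-treatment value in the categories 45 or more, 40 to below 45, and below 40, with the number below 40. Label it as a lowest-value count that does not itself confirm the protocol's 24-hour condition.

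The second table is promised in neither document. It is proposed because the normal-range shift cannot show movement across the protocol's own cut-points. If the sponsor prefers to omit the first, Section 7 should declare and justify that.

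The cost is SAP wording and two standard tables from data already collected. No clinical rule is changed or proposed.
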